### **6.7.5. TREATMENT PERIOD**

Treatment period start for medications, procedures and AEs is defined as:

- First administration of study drug.

Titration period start for AEs, medications and procedures is defined as:

- First administration of study drug.

Full treatment period start for AEs, medications and procedures is defined as:

- First administration of full treatment period study drug (i.e., second dose of 800 µg).

Treatment period end for medications, procedures and AEs is defined as:

- Last administration of study drug date plus 28 days.
- For AEs onset dates/times are recorded, so the calculation of period starts/ends will take account of both dates and times.

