Reference: CS\_WI\_BS005

Copyright © 2009, 2010, 2012, 2016 Quintiles Transnational Corp. All rights reserved.  
The contents of this document are confidential and proprietary to Quintiles Transnational Corp. Unauthorized use, disclosure or reproduction is strictly prohibited.

Number of dose compliance (%) = (Actual number of doses for the period / Protocol-specified number of doses for the period)\*100

- Dose amount compliance (%) will be derived per visit, for the titration and full treatment periods, as well as 'Overall' for the study.

Dose amount compliance (%) = (Actual amount of drug injected / Protocol-specified drug amount)\*100

Note that Dose Number 3 and 5 to 10 will include two intradermal injections; hence the compliance for dose number 3 and 5 to 10 will be derived based on the sum of the actual doses ( $\mu$ g) of the two intradermal injections. These doses will have a frequency count of one for the summary table.

Subjects will be assessed for exposure and compliance with respect to the dose and treatment period evaluated. Hence for a subject withdrawing after the first study drug dose, the subject will be included in exposure and compliance calculations for dose 1, titration period and overall only, and will not contribute to calculations for subsequent dose levels.

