## 15. SAFETY OUTCOMES

All safety analysis will be based on the ITT population.

Only descriptive summaries of the safety data will be provided as detailed in the latest version of the TLF shell document. All available safety data will be presented in by-subject listings.

There will be no statistical comparisons done between the dose levels for safety data.

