- Full treatment period: Any AE that started or worsened in severity on or after the first administration of full treatment period study drug (i.e., 2nd 800 µg dose) administration up to and including 28 days after last administration of study drug.

TEAEs are mutually exclusive for assignment to either the titration or full treatment periods. Note that the first dose at 800 µg is in the titration period, and the full treatment period starts with the second dose of 800 µg.

Relationship, as indicated by the Investigator, is classed as 'not related', 'possibly related', 'probably related' or 'definitely related' (increasing severity of relationship). A drug-related AE is defined as an AE with a relationship to study drug of 'possibly related', 'probably related' or 'definitely related' or with a missing or unknown relationship to study drug. If a subject reports an AE more than once within that SOC and/or PT, the AE with the highest related assessment will be used in the corresponding summaries of relatedness.

Severity is classed as 'mild', 'moderate' or 'severe' (increasing severity). AEs with a missing severity will be classified as 'severe' (worst case). If a subject reports an AE more than once within that SOC and/or PT, the AE with the worst case severity will be used in the corresponding severity summaries.

See Appendix 2: Partial Date/Time Conventions for handling of partial dates/times for AEs. In cases where it is not possible to define an AE as treatment emergent or not, the AE will be classified by the worst case i.e. treatment emergent.

The following tables will be presented by dose level of study drug last received prior to onset of each individual subject's AE for the ITT population :

- An overview of the number and percentage (%) of subject and frequency of events will be provided for the following TEAEs per the dose levels per defined period (titration and full treatment periods) as well as overall:
  - TEAEs.
  - Drug related TEAEs.
  - Treatment-emergent serious adverse events (TESAEs).
  - Drug related TESAE.
  - TEAEs leading to death.
  - TEAEs leading to early study withdrawal.
  - TEAEs leading to dose interruption or suspension.

---

Document: ATX\_GD\_59 Final 1.0 SAP 28FEB2018.docx  
Author: [name]

Version Number: Final 1.0  
Version Date: 28FEB2018

Template No: CS\_TP\_BS016 Revision 4  
Effective Date: 01Apr2016

Reference: CS\_WI\_BS005

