Copyright © 2009, 2010, 2012, 2016 Quintiles Transnational Corp. All rights reserved.  
The contents of this document are confidential and proprietary to Quintiles Transnational Corp. Unauthorized use, disclosure or reproduction is strictly prohibited.

- o Treatment emergent intradermal injection related reactions (Note such TEAEs will also be included in all other relevant categories, but broken out separately in addition).
  - o TEAEs by maximum severity.
- In addition to the overview of TEAEs, the following Incidence and frequency of TEAEs will be presented by SOC and PT. If an AE occurs more than once the subject will be counted once per MedDRA SOC and PT as relevant. Percentage of subjects in each category will be calculated relative to the total number of subjects in the ITT population for the respective dose level/period, implying all subjects who received the study drug administration or part thereof in the relevant period.
  - o Incidence and Frequency of TEAEs.
  - o Incidence and Frequency of TEAEs related to study drug.
  - o Incidence and Frequency of TESAEs.
  - o Incidence and Frequency of TEAEs leading to dose interruption, suspension or early study withdrawal.
  - o Incidence and Frequency of Treatment emergent intradermal injection related reactions.
  - o Incidence and Frequency of TEAEs by maximum severity.
  - o Incidence and Frequency of Non-TEAEs commencing after 28 days post-treatment incorporating overview details (i.e., with the exception of dose interrupted/suspended).
  - o Incidence and Frequency of Non-TESAEs commencing after 28 days post-treatment.
  - o Incidence and Frequency of Non-TEAEs commencing after 28 days post-treatment, by maximum severity.

The denominator used for the calculation of percentage will be the number of subjects in the ITT population for the respective dose level/period for incidence calculations and the total number of events assigned to the dose level/period for frequency calculations.

- Listings of the following will be provided in section 14, Tables:
- Serious AEs leading to death: AEs leading to death are defined as AEs with an outcome recorded as 'Death' or serious event criteria recorded as 'Death' on the AEs eCRF.
- Serious AEs: A serious AE is defined as an AE with the result 'Yes' answered for the question 'Serious event' in the AEs eCRF.

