#### **15.1.1. INJECTION SITE REACTION DIARY RESULTS**

Injection site reactions captured on the diary card will be listed by subject and visit and include the AE number for reactions that are reported as AEs. Subjects were requested to complete the diary card for the first 3 days. If symptoms were still present after the 3 days, subjects would complete the diary until the symptoms had totally disappeared.

These data will be summarised as frequency counts for each grade of reaction parameter, by visit for the ITT population. In the event of more than one response per reaction parameter per visit per patient, only the most severe occurrence for each injection site reaction for each subject per visit will be counted.

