## APPENDIX 2. PARTIAL DATE/TIME CONVENTIONS

Imputed date/times will NOT be presented in the listings.

If Date/Time is available the following derivations will be applied:

- Pre-treatment AE (Screening period): Any AE that started or worsened in severity on or after informed consent and prior to the first administration of study drug.
- TEAE: Any AE that started or worsened in severity on or after the first administration of study drug up to and including 28 days after the last administration of study drug.
  - Titration dose level received prior to AE: Assign any AE that started or worsened in severity on or after that dose level received up to the date/time of the next dose level administration for each dose level, up to the first administration of full treatment period study drug (i.e., 2nd 800 µg dose).
  - Full treatment dose level received prior to AE: Assign any AE that started or worsened in severity on or after the first full treatment dose (i.e., 2nd 800µg dose) up to and including 28 days after the last administration of study drug.
- Non-TEAE commencing post-treatment: Any AE that started or worsened in severity more than 28 days after the last administration of study drug.

---

Document: ATX\_GD\_59 Final 1.0 SAP 28FEB2018.docx  
Author: [name]

Version Number: Final 1.0  
Version Date: 28FEB2018

Template No: CS\_TP\_BS016 Revision 4  
Effective Date: 01Apr2016

Reference: CS\_WI\_BS005

Copyright © 2009, 2010, 2012, 2016 Quintiles Transnational Corp. All rights reserved.  
The contents of this document are confidential and proprietary to Quintiles Transnational Corp. Unauthorized use, disclosure or reproduction is strictly prohibited.

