**Note:**

Only scheduled visits adherence applicable to the study is to be validated according to the relevant visit window below. Visits not in accordance with the table below are to be identified by means of a flag on the listing of study visits:

---

Document: ATX\_GD\_59 Final 1.0 SAP 28FEB2018.docx  
Author: [name]

Version Number: Final 1.0  
Version Date: 28FEB2018

Template No: CS\_TP\_BS016 Revision 4  
Effective Date: 01Apr2016

Reference: CS\_WI\_BS005

Copyright © 2009, 2010, 2012, 2016 Quintiles Transnational Corp. All rights reserved.  
The contents of this document are confidential and proprietary to Quintiles Transnational Corp. Unauthorized use, disclosure or reproduction is strictly prohibited.

Visit	Protocol Study Day	Deviation if outside	Visit Window relative to date of first study drug administration
Screening visit (Week -4: )	Day -28 to -1	+ 5 days	Week -4: Day -33 to Day -1
Study day 1 visit	1	Not applicable	
Dose titration period visits	Week 2: Day 14 Week 4: Day 28 Week 6: Day 42 Week 8: Day 56	± 3 days	Week 2: Day 11 to 17 Week 4: Day 25 to 31 Week 6: Day 39 to 45 Week 8: Day 53 to 59
Full dose Treatment visits	Week 10: Day 70 Week 12: Day 84 Week 14: Day 98 Week 16: Day 112 Week 18: Day 126	± 3 days	Week 10: Day 67 to 73 Week 12: Day 81 to 87 Week 14: Day 95 to 101 Week 16: Day 109 to 115 Week 18: Day 123 to 129
Follow-up visits (Week 22)	Week 22: Day 154	± 3 days,	Week 22: Day 151 to 157
Follow-up visits (Week 30)	Week 30: Day 210	± 7 days	Week 30: Day 203 to 217

Study day is calculated relative to the date of first administration of study drug and is only presented for subjects with a study drug administration date (see section 6.1 ).

The ET visit will be allocated to a scheduled visit according to the table above, where the ET visit has occurred in place of the scheduled visit and is within the relevant visit window. Any ET visits will be reviewed for allocation to a scheduled visit, at the DR meeting.

Document: ATX\_GD\_59 Final 1.0 SAP 28FEB2018.docx  
Author: [name]

Version Number: Final 1.0  
Version Date: 28FEB2018

Template No: CS\_TP\_BS016 Revision 4  
Effective Date: 01Apr2016

Reference: CS\_WI\_BS005

Copyright © 2009, 2010, 2012, 2016 Quintiles Transnational Corp. All rights reserved.  
The contents of this document are confidential and proprietary to Quintiles Transnational Corp. Unauthorized use, disclosure or reproduction is strictly prohibited.

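### Adverse-event incidence by dose level ignores unequal exposure: the full-treatment 800 µg column covers 84 days and five doses, the titration 800 µg column 14 days and one dose

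*SAP*

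**What the plan says.** SAP 15.1 presents treatment-emergent events by the dose level last received before onset, separately for titration and full treatment. For percentages, the denominator "will be the number of subjects in the ITT population for the respective dose level/period for incidence calculations". A subject counts once per system organ class and preferred term. The percentage attached to event frequency uses the total events in the same column, so it is a share of events and not a rate.

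The 800 µg level appears twice. The first 800 µg dose "is in the titration period, and the full treatment period starts with the second dose of" 800 µg. Under Appendix 2, each titration level collects events only until the next dose level. The full-treatment rule reads "Assign any AE that started or worsened in severity on or after the first full treatment dose"; it runs to 28 days after the last dose and is not split by dose number. Section 6.7.5 sets the end of the treatment period at "Last administration of study drug date plus 28 days".

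On injections, Section 13 states "Note that Dose Number 3 and 5 to 10 will include two intradermal injections". Diary-card reactions are handled differently: Section 15.1.1 has them "summarised as frequency counts for each grade of reaction parameter, by visit for the ITT population". Section 15 adds: "There will be no statistical comparisons done between the dose levels for safety data".

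**The concern.** Adverse-event occurrence is one of the safety endpoints listed under the primary objective. With no formal comparison between dose levels, readers will compare the columns by eye. The most natural comparison is between the two 800 µg columns, because the dose is the same and only the repetition differs. A step up from titration to full treatment would look like an effect of repeat dosing. The full-treatment column would show such a step even with no drug effect, because a subject has far longer to have a first event there. Event counts grow with exposure in the same way.

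The affected area is narrow. The five titration columns have equal nominal time, so time at risk creates no trend from 25 to 800 µg. Diary reactions are already shown by visit, so the injection point concerns only the table of adverse-event-recorded injection-related reactions.

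**Working it through.** **Schedule.** Doses are 14 ± 3 days apart (protocol synopsis, Methodology; SAP 4.1). SAP Appendix 4, section 4.2 gives "Week 10: Day 70 Week 12: Day 84 Week 14: Day 98 Week 16: Day 112 Week 18: Day 126" and places Week 22 at Day 154. Ten doses span nine intervals: 9 × 14 = 126, and 126 + 28 = 154. This reproduces the plan's Week 22 day.

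**Exposure per column, for a subject who continues.**

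| Column | Days at risk | Doses | Injections |
|---|---|---|---|
| Titration 25 / 50 / 100 / 400 / 800 µg, each | 14 (11 to 17) | 1 | 1 / 1 / 2 / 1 / 2 |
| Full treatment 800 µg | 126 + 28 − 70 = 84 | 5 | 5 × 2 = 10 |

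The single injections at doses 1, 2 and 4 are inferred from Section 13, which lists only doses 3 and 5 to 10 as having two. Using the ±3-day windows at Weeks 10 and 18, full treatment lasts from 123 + 28 − 73 = 78 to 129 + 28 − 67 = 90 days. Against the 800 µg titration column the ratios are 84/14 = 6 for time and 5 for doses and injections.

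**Effect on incidence with no drug effect.** The documents give no event rate, so the risk p per 14 days is an assumption. A titration column reads p. Full treatment spans six such intervals and, if they are independent, reads 1 − (1 − p)^6. Clustering within subjects is modelled as beta-binomial with intra-subject correlation ρ.

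| p per 14 days | Titration column | Full treatment, independent | ρ = 0.2 | ρ = 0.5 | ρ = 1 |
|---|---|---|---|---|---|
| 5% | 5% | 26% | 18% | 12% | 5% |
| 10% | 10% | 47% | 34% | 22% | 10% |
| 20% | 20% | 74% | 58% | 41% | 20% |

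At p = 10%, independent, with the roughly 15 subjects expected to be dosed: 15 × 0.10 = 1.5 subjects versus 15 × 0.469 = 7.0.

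**Other contrasts at 10%, independent.**
- Whole titration (70 days) versus full treatment (84 days): 1 − 0.9^5 = 41% versus 47%, a mild difference.
- A subject who stops during titration carries 28 days at the last level received: 1 − 0.9^2 = 19% instead of 10%.
- Adverse-event-recorded injection reactions at an assumed 10% per dosing visit: 10% for one visit versus 1 − 0.9^5 = 41% over five (31% at ρ = 0.2, 21% at ρ = 0.5).

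**What a rate does.** With p = 10%, the constant event rate is −ln(0.9) = 0.105 per subject per 14 days, the same in both columns. For acute post-injection events with a constant risk per dose, however, events per day are 5/84 under full treatment and 1/14 under titration. The ratio is (5/84)/(1/14) = 0.833, so subject-time rates would read 17% lower under full treatment. Those events need a per-dose denominator.

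**The case against.** The tables are descriptive, nothing is tested between dose levels, and the columns are labelled by period. Event counts are planned, Section 13 summarises the number of doses per period, and the adverse-event listings give the last dose and the time since it. With about 15 subjects, a careful reader could work out events per dose. The table shells are not among the documents and might contain an exposure row. Rates would also not isolate a repeat-dosing effect, because every subject follows the same ascending sequence and full treatment stays confounded with calendar time and cumulative dose. Finally, the size of the artefact depends on assumed risks and vanishes with complete clustering. An event that persists unchanged from titration is not counted again, which the constant-risk model leaves out.

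Much of this stands as a limit on the point: no test is invalidated, the magnitude is illustrative, and the confounding remains after adjustment. But the absence of a test leaves the two 800 µg columns side by side. Section 13 gives doses, not days at risk tied to the event columns. Asking readers to rebuild rates from listings is no substitute for showing them, and shells not seen cannot be assumed to do so.

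**Conclusion.** The concern holds. The single-level columns in the adverse-event tables do not have comparable exposure, and the planned n (%) cannot distinguish a repeat-dosing effect from longer observation. The exposure ratios (6 times the time, 5 times the doses) follow directly from the SAP for subjects who complete dosing on schedule. The size in percentage points rests on assumed risks: for a 10% risk per 14 days and no drug effect, full treatment would read between 10% (complete clustering) and 47% (independence). The problem lies in the contrast of full treatment with single titration levels, above all at 800 µg; it does not affect the trend across titration levels or the diary tables. It is a foreseeable misreading of primary-objective safety tables that is cheap to prevent.

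**What to change.** In SAP 15.1 and the matching shells:

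- Keep the planned n (%), and add to every dose-level/period column the subject-days at risk and the events per 100 subject-days.
- For adverse-event-recorded injection-related reactions, add the number and percentage of dosing visits (or injections) with a reaction.
- If full treatment is split by dose number 6 to 10, truncate dose 10 at 14 days or show its Days 15 to 28 separately. Treat the last dose of subjects who stop early in the same way.
- State that acute post-injection events are to be read from the per-dose rows, because of the 17% dilution shown above.
- Note that rates remove the difference in observation time but not the confounding of dose with time in a fixed ascending sequence.

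The programming effort is small: dose dates, onset dates and times, and dose counts are already collected. The price is a few extra table rows and the assumption of a roughly constant hazard behind the subject-time rates.

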- Results from the physical examination, and vital signs (reported on an ongoing basis and compared to baseline/screening).
- Premature termination and reasons for premature termination from treatment and/or the study.

Criteria for Evaluation of the Secondary Objectives:

- TSHR antibody levels.
- Ratio of stimulatory vs inhibitory TSHR antibodies.
- Free T3, free T4 and TSH serum levels.

Criteria for Evaluation of the Exploratory Objectives:

- TSHR induced PBMC T cell activity.
- T-cell cytokine signature.
- IL-10 pathway and associated genes (mRNA).

Statistical Considerations

A Statistical Analysis Plan (SAP) will be finalised prior to database lock describing details of analyses to be performed on all endpoints for the final analysis. Example tabulations and listings will also be included in this plan.

- All the data will be listed
- All relevant data will be summarised and tabulated in the most appropriate manner.

The statistical methods used will be appropriate to the objectives of the study and the nature of the data.

No formal sample size calculation has been performed. 12 evaluable subjects is considered a sufficient and adequate number of subjects to explore the defined safety aspects of the study and provide data about potential efficacy.

Study Population

The Study population corresponds to all enrolled subject, i.e. all subjects eligible for enrolment into the study.

All data listings will be based on the Study population.

Intention-To-Treat (ITT)/Safety Population

A primary ITT population will be defined for use in presenting baseline, efficacy and safety data. The ITT population corresponds to all subjects who received at least one administration of study drug at any time during the study, irrespective of compliance with eligibility and other protocol criteria.

The Safety population will be denoted as the 'ITT population' for the summarisation of safety endpoints.

Per-Protocol Population (PP)

A per-protocol (PP) population will be used to also consider all efficacy data, and is defined as all ITT subjects who complied with the protocol requirements. Subjects will need to have complied with the protocol (i.e. no major protocol deviations) up to and including the Week 22 visit, criteria to include (but not limited to):

- Met all inclusion and exclusion criteria on study entry,

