## 3. STUDY OBJECTIVES

### 3.1. PRIMARY OBJECTIVE

The primary objective is to evaluate whether ATX-GD-59 administration every two weeks by intradermal injection is safe and well tolerated in male and female subjects with Graves' disease, not currently treated with anti-thyroid therapy.

Safety endpoints, that will be evaluated on an ongoing basis up to Week 22 (i.e., 28 days post last study medication dose), are:

- Injection site reactions as reported by the subjects in the diary card.
- Occurrence of treatment related Adverse Events (AEs), Serious Adverse Events (SAEs), and laboratory abnormalities compared to baseline.
- Results from the physical examination, and vital signs (reported on an ongoing basis and compared to baseline).
- Early withdrawal and reasons for early withdrawal from treatment and/or the study.

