- AEs leading to early study withdrawal: AEs leading to early study withdrawal are defined as AEs with action taken as 'Subject withdrawn from study' on the AEs eCRF.
- AEs leading to dose interruption or suspension: AEs will be captured on the AE and SAE eCRF where 'Action taken with study treatment' is indicated as 'Study treatment permanently stopped' or 'Study treatment interrupted'.

---

Document: ATX\_GD\_59 Final 1.0 SAP 28FEB2018.docx  
Author: [name]

Version Number: Final 1.0  
Version Date: 28FEB2018

Template No: CS\_TP\_BS016 Revision 4  
Effective Date: 01Apr2016

Reference: CS\_WI\_BS005

Copyright © 2009, 2010, 2012, 2016 Quintiles Transnational Corp. All rights reserved.  
The contents of this document are confidential and proprietary to Quintiles Transnational Corp. Unauthorized use, disclosure or reproduction is strictly prohibited.

The AEs data will also be presented in the following by-subject listings and include all AEs as reported from the signing of informed consent until the end of the study for the Study population:

- All AEs reported in the study together with all details, including flags for pre-treatment, TEAEs, Non-TEAEs, SAEs, injection site related and Graves' disease symptoms AEs and a flag for any subjects with no AEs reported.
- Pre-treatment AEs, TEAEs, non-TEAEs commencing post-treatment (other than Grave's disease and injection site reactions for each one), and Graves' disease symptoms and intradermal injection site related reactions will be listed separately.
- Intradermal injection related reactions will be captured on the AE and SAE eCRF where 'Is the event an intradermal injection related reaction?' is indicated as 'Yes'. The site of last injection prior to the AE will be listed on the injection site reactions listing.
- Graves' disease symptoms will be captured where 'Causes of the event other than study drug' on the AE eCRF is indicated as 'Disease under study' and intradermal injection related reaction is not 'Yes'. Any with unknown cause will be listed as TEAEs and will not be listed as Graves' disease symptoms.

AE listings will include all details collected on the AE eCRF and additionally, time (days, hrs, mins) since last dose and a flag for period for TEAEs (titration, full treatment), last dose received prior to the AE and duration of the AE (calculated as resolution date – onset date of the AE + 1 day, and presented as Days).

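### SAP 15.1 classes adverse events that permanently stop study treatment as dose interruption or suspension, so the AE summary tables mislabel them and do not tabulate permanent discontinuation separately

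*SAP*

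**What the plan says.** The protocol synopsis lists this safety endpoint under the primary objective: "Premature termination and reasons for premature termination from treatment and/or the study". SAP 3.1 repeats it as "Early withdrawal and reasons for early withdrawal from treatment and/or the study".

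SAP 15.1 defines two AE categories that bear on it:

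- **Interruption or suspension.** The definition begins "AEs leading to dose interruption or suspension: AEs will be captured on the AE and SAE eCRF where" and sets the condition "Action taken with study treatment' is indicated as 'Study treatment permanently stopped' or 'Study treatment interrupted".
- **Study withdrawal.** "AEs leading to early study withdrawal are defined as AEs with action taken as 'Subject withdrawn from study' on the AEs eCRF".

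The TEAE overview, presented by dose level last received, has a row for each: "TEAEs leading to early study withdrawal" and "TEAEs leading to dose interruption or suspension". By SOC and PT there is one combined output: "Incidence and Frequency of TEAEs leading to dose interruption, suspension or early study withdrawal". The listings placed with the section 14 tables use the same two definitions.

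SAP 9 works differently. Its disposition summary counts early discontinuation of treatment separately from early withdrawal from the study, with primary reasons for each. The disposition listing adds the last dose received and whether it was a titration or full-treatment dose.

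**The concern.** A permanent stop and a temporary interruption are opposite outcomes for tolerability, yet they share one category, and its name describes only the temporary one. The neighbouring category does not catch the permanent stop either, because it requires the subject to have left the study. SAP 9 treats leaving treatment and leaving the study as different events, so the plan itself allows for a subject who stops dosing and stays in follow-up. In the AE summaries, that subject is reported as an interruption.

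SAP 4.1 describes a first-in-human study with within-subject dose escalation. The events that end dosing, and the dose level at which they occur, are among the main things a reader looks for in its AE tables. The outputs can also appear to disagree: disposition could show subjects stopping treatment early, while the AE overview shows no study withdrawals and only interruptions.

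**Working it through.** The plan states no figure on this point, so the main check is textual: follow three kinds of subject through the planned outputs.

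| Subject | AE overview (15.1) | SOC/PT table (15.1) | Section 14 listing heading | Disposition table (9) |
|---|---|---|---|---|
| A: stops dosing for good because of an AE, stays in follow-up | Interruption or suspension | Combined table | Interruption or suspension | Treatment discontinuation, with primary reason |
| B: dosing interrupted because of an AE, then resumed | Interruption or suspension | Combined table | Interruption or suspension | Not a discontinuation |
| C: withdrawn from the study because of an AE | Study withdrawal | Combined table | Study withdrawal | Study withdrawal, with primary reason |

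A and B fall in the same cell in all three AE outputs. In the SOC/PT table C joins them. Only the disposition table separates A from B in a summary.

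**Size of one row.**

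- Inputs: the protocol synopsis expects about 15 subjects to receive at least one dose and about 12 to complete dosing and attend Week 22. SAP 15.1 bases percentages on the subjects dosed in the relevant dose level or period, so 15 approximates the overall denominator and 12 the late dose levels.
- One subject: 1/15 = 6.7% and 1/12 = 8.3%, shown as 7% and 8% under the whole-number rounding in SAP 6.6.
- The planning numbers leave 15 − 12 = 3 treated subjects who do not complete, for any reason. As an illustration, suppose three subjects have a qualifying event: 3/15 = 20% and 3/12 = 25%.
- Three permanent stops and three interruptions give the same overview row: 3 subjects, 20 to 25%. In the disposition table they differ: 3 treatment discontinuations against 0.

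**What the disposition table covers.** It gives the count and the primary reason. SAP 9 does not list the reason categories, and it does not describe the table as broken down by preferred term, relatedness, severity or dose level.

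**The case against.** The strongest reply is that nothing is lost. The endpoint in SAP 3.1 is withdrawal and its reasons, and SAP 9 summarises exactly that, with treatment and study kept apart. The disposition listing gives the last dose. The AE listings carry all fields on the AE eCRF, plus last dose, period and time since dose, so the event that ended dosing can be identified along with its recorded severity and relatedness. With about 15 treated subjects, reading listings is practical. All presentations are descriptive, so no estimate or test is biased.

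This stands, and it limits the point. A reader might infer that AE-driven treatment discontinuation is summarised nowhere, or that a component of the primary objective goes unreported. The documents do not support that: SAP 9 counts it by primary reason, and the listings allow event-level recovery.

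Two further replies carry less weight:

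- *Suspension* may have been meant to cover permanent stops. In ordinary use the word suggests a pause, and even on that reading the row still pools the two outcomes.
- SAP 8 and 15 leave table layout to the table, listing and figure (TLF) shells, which are not among the documents reviewed and might split the row. They would not correct a definition stated in the SAP text itself.

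**Conclusion.** Wrong as written, minor. The SAP 15.1 definition puts permanent treatment stops under a label for temporary ones. As a result, no AE summary described there separates TEAEs that ended treatment from those that only interrupted it. Treatment discontinuation is counted only in the disposition table, by primary reason, and event detail is left to listings. Each affected subject is about 7 to 8% of a row in which the two outcomes cannot be told apart.

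This rests on three assumptions:

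- The eCRF codes are used as SAP 15.1 describes them.
- At least one subject stops dosing because of an AE and stays in the study; the documents give no expected number. If none does, the wording is still wrong but no such subject is mislabelled.
- The TLF shells follow the SAP text.

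**What to change.** Replace the pooled definition in SAP 15.1 with three categories taken from the existing eCRF codes:

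1. *TEAEs leading to permanent discontinuation of study drug*: the permanent-stop code.
2. *TEAEs leading to dose interruption*: the interruption code.
3. *TEAEs leading to early study withdrawal*: as now defined.

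Show these as separate rows in the overview, and as separate categories in the SOC/PT table and the section 14 listings. State how an event is counted if it carries both the permanent-stop and the study-withdrawal codes, since the SAP does not say whether they can occur together.

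Reconcile the number of subjects in category 1 with those whose primary reason for treatment discontinuation in the disposition table is an adverse event, and explain any difference. The two may legitimately differ, because disposition allows one primary reason per subject.

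The cost is an edit to one definition and to the matching shells, plus a few rows repeated across dose levels and periods. In a study of this size many will be sparse or empty. No new data are needed and no clinical rule changes.
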